3.1.6.2 Rituximab

This clinical trial will utilize the approved dose of rituximab for relapsed/refractory low-grade of follicular B-cell NHL, 375 mg/m2 weekly for 4 weeks.²³ Premedication for prophylaxis against hypersensitivity reactions will be administered per clinical standard of care on initial and subsequent infusions, with modifications permitted at investigator discretion.

3.1.6.3 Obinutuzumab

3.1.7 The third arm, Arm C, will combine obinutuzumab with pembrolizumab and will use obinutuzumab: 1000 mg weekly for 4 weeks then up to 6 additional doses (maximum 10 doses) at 1000 mg every 3 months, for patients achieving response (PR/CR) or SD with clinical benefit. Clinical benefit in the setting of stable disease per Lugano criteria will be assessed by the treating investigator. The obinutuzumab dose is identical to the approved dosing in relapsed follicular lymphoma (in combination with benadamustine³¹), although this study will employ a less frequent interval (q 3 months) and lower overall dose (maximum 6 doses extended therapy). Every 3-month dosing is supported by the initial phase I study

of obinutuzumab, and limiting the duration to a maximum of 6 additional doses may impart a more favorable risk/benefit ratio.³³Rationale for Endpoints

3.1.7.1 Efficacy Endpoints

The primary endpoint is overall response rate assessed independently for each arm: relapsed/refractory FL (Arms A and C), and relapsed/refractory DLBCL (Arm B). Overall response rate is defined as the rate of complete + partial responses using CT criteria (Lugano 2014).²⁸

3.1.7.2 Biomarker Research

Tissue-based assays for tumor and immune infiltrate expression of PD1, PD-L1 will be performed by a third party laboratory to be designated by Merck, with tissue received from the most recent biopsy specimen when available.

Patients may undergo an optional tumor biopsy at baseline and up to one time between cycles 1 and 3. Patients may also undergo optional biopsies in the setting of persistent or relapsed disease. Correlative studies will evaluate the tumor microenvironment.

For all patients, baseline and serial evaluation of peripheral blood T cell populations by flow cytometry will be undertaken. In previous studies, alterations of both PD-L1 and PD1 bearing lymphocytes have been observed in peripheral blood. This study will analyze markers including (but not limited to) CD3, CD4, CD8, CD14, PD-1, PD-L1, and PDL-2 on peripheral blood mononuclear cells, and will explore whether alterations in T cell subsets occur with therapy and predict outcomes with treatment.

4.0 METHODOLOGY

4.1 Entry Criteria

4.1.1 Diagnosis/Condition for Entry into the Trial

Patients 18 years of age or older with relapsed/refractory FL, or relapsed/refractory DLBCL relapsing after, ineligible for, or declining autologous stem cell transplant, are eligible for this trial. Relapsed is defined as having achieved remission but then experienced progression of the malignancy. Refractory is defined as failing to attain a remission after therapy.

4.1.2 Subject Inclusion Criteria

In order to be eligible for participation in this trial, the subject must:

- 1. Have relapsed/refractory DLBCL or relapsed/refractory FL.
 - a. For DLBCL, patients must have relapsed after, declined, or considered ineligible for high-dose chemotherapy and autologous stem cell transplantation.

- b. For FL, in addition to relapsed/refractory disease status, patients must have received therapy with CD20 antibody-directed therapy, and must have an indication for treatment. FL eligibility also requires patients have no standard options with curative potential, nor options with more favorable risk/benefit ratio in the judgment of the investigator.
- c. For FL Arm C (obinutuzumab + pembrolizumab), patients must have relapsed/refractory disease after rituximab-containing therapy including:
 - i. Rituximab in combination with chemotherapy (at 1 prior line) or
 - ii. ≥ 2 prior lines of therapy
 - iii. Patients may have no standard options with curative potential, nor options with more favorable risk/benefit ratio in the judgment of the investigator.
- 2. Be willing and able to provide written informed consent/assent for the trial.
- 3. Be \geq 18 years of age on day of signing informed consent.
- 4. Have measurable disease (1.5 cm or greater in the longest diameter of nodal or extranodal disease).
- 5. Have a performance status of 0 or 1 on the ECOG Performance Scale.
- 6. Demonstrate adequate organ function as defined in table 1 below, with screening labs to be performed within 28 days of cycle 1 day 1.

System	Laboratory Value
Hematological	
Absolute neutrophil count (ANC)	≥500/μL ^{a, b}
Platelets	≥25 000/µL ^{a, b}
Hemoglobin	$\geq 8 \text{ g/dL}^{\text{a,b}}$
Renal	
Creatinine OF	$\underline{\mathbf{R}} \leq 1.5 \times \text{ULN} \underline{\mathbf{OR}}$
Measured or calculated ^c creatining clearance	$\geq 30 \text{ mL/min}$ for participant with creatinine levels >1.5 × institutional ULN
(GFR can also be used in place o creatinine or CrCl)	f
Hepatic	
Total bilirubin	≤1.5 ×ULN OR direct bilirubin ≤ULN for participants with total bilirubin levels >1.5 × ULN
AST (SGOT) and ALT (SGPT)	\leq 2.5 × ULN (\leq 5 × ULN for participants with liver metastases)

 Table 1 Adequate Organ Function Laboratory Values

Protocol v4.0 dated 21 July 2021

Coagulation				
International normalized ratio	$\leq 1.5 \times ULN$ unless participant is receiving			
(INR) OR prothrombin time (PT)	anticoagulant therapy as long as PT or PTT is			
Activated partial thromboplastin	within therapeutic range of intended use of			
time (aPTT)	anticoagulants			
ALT (SGPT)=alanine aminotransferase	(serum glutamic pyruvic transaminase);			
AST (SGOT)=aspartate aminotransferase	(serum glutamic oxaloacetic transaminase);			
GFR=glomerular filtration rate; ULN=upper limit of normal.				
^a Growth factor and/or transfusion support is permissible to stabilize participant prior to study				
treatment if needed.				
^b No lower limit if cytopenia is related to bone	e marrow involvement.			
^c Creatinine clearance (CrCl) should be calcul	*			
Note: This table includes eligibility-defining laboratory value requirements for treatment;				
laboratory value requirements should be adapted according to local regulations and guidelines				
for the administration of specific chemothera	pies.			

- 7. Female subjects of childbearing potential (Section 4.4.2) should have a negative urine or serum pregnancy within 72 hours prior to receiving the first dose of study medication. If the urine test is positive or cannot be confirmed as negative, a serum pregnancy test will be required.
- 8. Female subjects of childbearing potential (Section 4.4.2) must be willing to use an adequate method of contraception as outlined in Section 4.4.2 Contraception, for the course of the study until at least 12 months after the last dose of study therapy.

Note: Abstinence is acceptable if this is the usual lifestyle and preferred contraception for the subject.

9. Male subjects of childbearing potential (Section 4.4.2) must agree to use an adequate method of contraception as outlined in section 4.4.2 starting with the first dose of study therapy until at least 12 months after the last dose of study therapy.

Note: Abstinence is acceptable if this is the usual lifestyle and preferred contraception for the subject.

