3.1.2 Background: Relapsed/Refractory Diffuse Large B Cell Lymphoma

Patients with relapsed/refractory DLBCL ineligible for, or progressing after, autologous transplant lack a uniform recommended treatment approach. Standard therapy is largely palliative³ and allogeneic transplant is associated with long-term survival in about 25% of patients, with non-relapse mortality occurring in 36-56% depending on conditioning regimen.¹⁷ Novel therapies are needed for this high risk subgroup. Rituximab as a single agent showed a 37% overall response rate in relapsed, rituximab-naïve DLBCL and was well-tolerated with typical infusion reactions comprising most adverse events.¹⁸ Rituximab efficacy in patients previously exposed to rituximab appears lower, based on data from its use as a component of salvage chemotherapy, particularly among patients who relapse within a year of diagnosis.^{19,20} Therefore, while rituximab is tolerable for relapsed DLBCL, its single agent activity modern cohorts who will have received first-line rituximab-containing chemoimmunotherapy is likely to be modest. Combination therapy with pembrolizumab may improve the efficacy of rituximab therapy for relapsed DLBCL patients failing or ineligible for transplant, while avoiding risk posed by chemotherapeutic regimens.

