4.1.3 Subject Exclusion Criteria

The subject must be excluded from participating in the trial if the subject:

1. Is currently participating and receiving study therapy or has participated in a study of an investigational agent and received study therapy or used an investigational device within 4 weeks of the first dose of treatment.

- 2. Has a diagnosis of immunodeficiency or is receiving systemic steroid therapy or any other form of immunosuppressive therapy within 7 days prior to the first dose of trial treatment, except for physiologic corticosteroid replacement therapy for adrenal or pituitary insufficiency which is permitted.
- 3. Has a known history of active TB (Bacillus Tuberculosis)
- 4. Hypersensitivity to pembrolizumab or any of its excipients.
- 5. Has had a prior anti-cancer monoclonal antibody (mAb) within 4 weeks prior to study Day 1 or who has not recovered (i.e., ≤ Grade 1 or at baseline) from adverse events due to agents administered more than 4 weeks earlier.
- 6. Prior allogeneic transplant, within the last 5 years.
- 7. Has had prior chemotherapy, targeted small molecule therapy, or radiation therapy within 2 weeks prior to study Day 1 or who has not recovered (i.e., ≤ Grade 1 or at baseline) from adverse events due to a previously administered agent.
 - Note: Subjects with \leq Grade 2 neuropathy are an exception to this criterion and may qualify for the study.
 - Note: If subject received major surgery, they must have recovered adequately from the toxicity and/or complications from the intervention prior to starting therapy.
- 8. Has a known additional malignancy that is progressing or requires active treatment. Exceptions include basal cell carcinoma of the skin or squamous cell carcinoma of the skin that has undergone potentially curative therapy or in situ cervical cancer.
- 9. Has known active central nervous system (CNS) metastases and/or lymphomatous meningitis. Subjects with previously treated brain metastases or lymphomatous meningitis may participate provided they are stable (without evidence of progression by imaging for at least four weeks prior to the first dose of trial treatment and any neurologic symptoms have returned to baseline), have no evidence of new or enlarging brain metastases, and are not using steroids for at least 7 days prior to trial treatment.

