7.1.2. Arm B: Relapsed/refractory DLBCL

The following assumptions will underlie the two-stage design for Arm B: At the end of induction response rate will be 50% with this combination, against a null hypothesis of 20%. With this 2-stage design, 9 patients will be enrolled in the first stage. If 2 or fewer respond among these 9 patients, accrual to this study arm will be stopped. Otherwise, 8 additional patients will be accrued in the second stage for a total of 17. The null hypothesis will be rejected if 7 or more responses are observed in 17 patients. This design yields a type I error rate of .05 and a power of .8 when the true response is 50%.

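### Arm B does not require prior CD20-directed therapy, so rituximab-naive DLBCL patients, whose cited response to rituximab alone exceeds the 20% null, can count toward its success rule

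*Combined protocol and SAP*

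**What the plan says.** Section 4.1.2, criterion 1a, sets the DLBCL entry condition: "For DLBCL, patients must have relapsed after, declined, or considered ineligible for high-dose chemotherapy and autologous stem cell transplantation". All of it concerns transplant. For follicular lymphoma, criterion 1b adds a treatment-history condition: "patients must have received therapy with CD20 antibody-directed therapy, and must have an indication for treatment". Criterion 1c goes further for Arm C and asks for disease that is relapsed or refractory after a rituximab-containing regimen.

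No other section supplies the missing condition for Arm B. Sections 4.1.1 and 7.0 describe the DLBCL group by transplant status only. The one exclusion in section 4.1.3 that concerns earlier antibody treatment is a washout, "Has had a prior anti-cancer monoclonal antibody (mAb) within 4 weeks prior to study Day 1", which limits how recent the exposure may be but does not require any.

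Section 3.1.2 separates two kinds of patient. For the unexposed it reports: "Rituximab as a single agent showed a 37% overall response rate in relapsed, rituximab-naïve DLBCL". For the exposed it gives no figure. It says that efficacy appears lower and that single-agent activity in "modern cohorts who will have received first-line rituximab-containing chemoimmunotherapy is likely to be modest".

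Section 7.1.2 states the Arm B hypotheses: "At the end of induction response rate will be 50% with this combination, against a null hypothesis of 20" per cent. The arm stops if 2 or fewer of the first 9 patients respond. Otherwise 8 more are enrolled, and success is 7 or more responses in 17. The stated type I error is .05, with power .8 at 50%.

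**The concern.** Arm B has no concurrent control, so the 20% benchmark does the work of one. It is meaningful only if the enrolled patients are of the kind it describes. The rationale describes patients who have already had rituximab, but the entry criteria also admit patients who have not. For those patients the protocol's own background gives a rate on the antibody backbone alone that is nearly twice the null (37/20 = 1.85).

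What is at stake is attribution. Section 3.1.2 hopes that pembrolizumab will improve on rituximab. If rituximab-naive patients contribute to the 7 responses, a declared success is weaker evidence of that. Section 7 specifies no Arm B analysis by prior rituximab, so the primary result would not reveal the mixture.

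**Working it through.** **Inputs.** From section 7.1.2: n1 = 9, stop at 2 or fewer responses, 8 further patients, success at 7 or more of 17, null 20%, alternative 50%. From section 3.1.2: 37% for rituximab alone in naive disease. The documents do not give the number of naive patients (k) or the response rate in exposed patients (pE). Both are assumed here and varied.

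**Step 1: the plan's own figures.** With one true rate p for all patients,

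P(success) = Σ over x = 3 to 9 of P(X1 = x) × P(X2 ≥ 7 − x), where X1 ~ Bin(9, p) and X2 ~ Bin(8, p).

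At p = 0.20:

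| x | P(X1 = x) | P(X2 ≥ 7 − x) | product |
|---|---|---|---|
| 3 | 0.17616 | 0.05628 | 0.00991 |
| 4 | 0.06606 | 0.20308 | 0.01342 |
| 5 | 0.01652 | 0.49668 | 0.00820 |
| 6 | 0.00275 | 0.83223 | 0.00229 |
| 7 | 0.00029 | 1 | 0.00029 |
| 8 | 0.00002 | 1 | 0.00002 |

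The term for x = 9 is negligible. The total is 0.0341. The same sum at p = 0.50 is 0.806, which matches the stated power of .8. The stated .05 is therefore a ceiling that the rule respects with room to spare, not its exact value.

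**Step 2: k naive patients among 17.** Give k patients a response probability of 0.37 and the other 17 − k a probability of pE. If j of the naive patients fall in stage 1, X1 is a sum of j Bernoulli(0.37) and 9 − j Bernoulli(pE) variables, and X2 is a sum of k − j and 8 − k + j such variables. Apply the Step 1 rule and average over j with weights C(9, j) × C(8, k − j) / C(17, k).

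Worked case, k = 2 and pE = 0.20: the weights for j = 0, 1, 2 are 28/136, 72/136 and 36/136, and the success probabilities are 0.0505, 0.0528 and 0.0546. The weighted mean is 0.2059 × 0.0505 + 0.5294 × 0.0528 + 0.2647 × 0.0546 = 0.0528.

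Chance of success when nobody gains from pembrolizumab, with pE = 0.20:

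| naive of 17 | 0 | 1 | 2 | 3 | 4 | 5 |
|---|---|---|---|---|---|---|
| P(success) | 0.034 | 0.043 | 0.053 | 0.065 | 0.079 | 0.094 |

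**Step 3: sensitivity to the exposed rate.** Smallest number of naive patients that takes the chance above .05:

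| pE | naive patients needed | P(success) at that number | P(success) with 3 naive |
|---|---|---|---|
| 20% | 2 | 0.053 | 0.065 |
| 18% | 4 | 0.057 | 0.045 |
| 15% | 6 | 0.058 | 0.023 |
| 10% | 8 | 0.053 | 0.005 |

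**The case against.** The strongest reply is that the plan's .05 is a statement about a true rate of 20%, and there it is conservative. A reader might infer from the figures above that the stated type I error is wrong, or that it fails in the population admitted. The documents do not support that. With naive patients in the mix the average true rate exceeds 20%, so rejecting 20% is a correct statement about that mix. The figures are rejection probabilities at a different true rate. What suffers is the reading that the result exceeds what rituximab alone would have given.

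A reader might also infer that a handful of naive patients will inflate the success rate whatever else is true. That needs two things the documents do not provide. The first is the number of naive patients. Section 3.1.2 expects modern patients to have had first-line rituximab, so it is probably small; one such patient leaves the chance below .05, and two take it only to 0.053. The second is an exposed rate at or very near 20%. Section 7.1.2 gives no source for the 20%, and section 3.1.2 gives no exposed rate, so it is an inference that the null describes exposed patients. At 15% or 10%, three naive patients leave the chance well under .05.

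The 37% is also borrowed. The documents do not show that it applies to patients who declined, could not have or relapsed after transplant, assessed by CT criteria at the end of induction.

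Finally, section 6.1.1.5.2 has prior cancer treatments reviewed for every subject, so naive patients can be identified. That stands, but no Arm B analysis uses the information.

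These points limit the size of the problem. They do not supply the missing criterion.

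**Conclusion.** The gap is real and its consequence is conditional. Nothing in the entry criteria or the statistical section confines Arm B to patients with prior CD20-directed therapy, although the rationale presumes it and the follicular lymphoma criteria require it. The design arithmetic is sound: exact type I error is 0.034 at 20%, and power is 0.806 at 50%.

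If exposed patients respond at exactly 20% and naive patients at 37%, two naive patients bring the chance of success without any pembrolizumab effect to about the stated .05, and three to five raise it to between 0.065 and 0.094. With lower exposed rates the trial could absorb more naive patients before passing .05. Since the documents imply few naive patients, this is a modest risk to the interpretation of the primary result, worth closing because closing it costs so little.

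**What to change.** Add to criterion 1a, for DLBCL, the prior CD20-directed therapy condition that 1b already applies to follicular lymphoma. This is one line. The cost is that the occasional rituximab-naive patient is excluded, which section 3.1.2 suggests would be rare.

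If Arm B accrual is complete, leave the criterion as it stands. State how many of the Arm B patients were rituximab-naive, and report the response rate with and without them. The prior-treatment review in section 6.1.1.5.2 should hold what is needed, so no new data collection is called for. Section 7.1.2 should also say which population the 20% null describes and where it comes from.

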4.1.3 Subject Exclusion Criteria

The subject must be excluded from participating in the trial if the subject:

1. Is currently participating and receiving study therapy or has participated in a study of an investigational agent and received study therapy or used an investigational device within 4 weeks of the first dose of treatment.

- 2. Has a diagnosis of immunodeficiency or is receiving systemic steroid therapy or any other form of immunosuppressive therapy within 7 days prior to the first dose of trial treatment, except for physiologic corticosteroid replacement therapy for adrenal or pituitary insufficiency which is permitted.
- 3. Has a known history of active TB (Bacillus Tuberculosis)
- 4. Hypersensitivity to pembrolizumab or any of its excipients.
- 5. Has had a prior anti-cancer monoclonal antibody (mAb) within 4 weeks prior to study Day 1 or who has not recovered (i.e., ≤ Grade 1 or at baseline) from adverse events due to agents administered more than 4 weeks earlier.
- 6. Prior allogeneic transplant, within the last 5 years.
- 7. Has had prior chemotherapy, targeted small molecule therapy, or radiation therapy within 2 weeks prior to study Day 1 or who has not recovered (i.e., ≤ Grade 1 or at baseline) from adverse events due to a previously administered agent.
 - Note: Subjects with \leq Grade 2 neuropathy are an exception to this criterion and may qualify for the study.
 - Note: If subject received major surgery, they must have recovered adequately from the toxicity and/or complications from the intervention prior to starting therapy.
- 8. Has a known additional malignancy that is progressing or requires active treatment. Exceptions include basal cell carcinoma of the skin or squamous cell carcinoma of the skin that has undergone potentially curative therapy or in situ cervical cancer.
- 9. Has known active central nervous system (CNS) metastases and/or lymphomatous meningitis. Subjects with previously treated brain metastases or lymphomatous meningitis may participate provided they are stable (without evidence of progression by imaging for at least four weeks prior to the first dose of trial treatment and any neurologic symptoms have returned to baseline), have no evidence of new or enlarging brain metastases, and are not using steroids for at least 7 days prior to trial treatment.
- 10. Has active autoimmune disease that has required systemic treatment in the past 2 years (i.e. with use of disease modifying agents, corticosteroids or immunosuppressive drugs). Replacement therapy (e.g. thyroxine, insulin, or physiologic corticosteroid replacement therapy for adrenal or pituitary insufficiency, etc.) is not considered a form of systemic treatment.
- 11. Has known history of, or any evidence of active, non-infectious pneumonitis/interstitial lung disease.

12. Has an active infection requiring systemic therapy. Protocol v4.0 dated 21 July 2021

- 13. Has a history or current evidence of any condition, therapy, or laboratory abnormality that might confound the results of the trial, interfere with the subject's participation for the full duration of the trial, or is not in the best interest of the subject to participate, in the opinion of the treating investigator.
- 14. Has known psychiatric or substance abuse disorders that would interfere with cooperation with the requirements of the trial.
- 15. Is pregnant or breastfeeding or expecting to conceive or father children within the projected duration of the trial, starting with the pre-screening or screening visit until at least 12 months after the last dose of study treatment.
- 16. Has received prior therapy with an anti-PD-1, anti-PD-L1, or anti-PD-L2 agent.
- 17. Has a known history of Human Immunodeficiency Virus (HIV) (HIV 1/2 antibodies).
- 18. Has known active Hepatitis B (e.g., HBsAg reactive) or Hepatitis C (e.g., HCV RNA [qualitative] is detected).
- 19. Has received a live vaccine or live-attenuated vaccine within 30 days of planned start of study therapy. Administration of killed vaccines is allowed.

Note: Seasonal influenza vaccines for injection are generally inactivated flu vaccines and are allowed; however intranasal influenza vaccines (e.g., Flu-Mist®) are live attenuated vaccines, and are not allowed.

